12.1 Documenting, Recording, and Reporting Adverse Events

All AEs occurring from the time of the initial leukapheresis through week 48 will be documented, recorded, and reported. If no leukapheresis is performed, then all AEs occurring from the time of pembrolizumab administration through week 48 will be documented, recorded, and reported. Between weeks 48 and 96, reporting will be limited to only those SAEs and autoimmune events that are possibly, probably, or definitely related to pembrolizumab.

At each contact with the participant, information regarding AEs will be elicited by appropriate questioning and examinations and will be:

- documented in the participant's medical record/source document,
- recorded in CRIMSON, and
- reported as outlined below (e.g., IND sponsor and FDA).

If a diagnosis is clinically evident (or subsequently determined), then the diagnosis rather than the individual signs and symptoms or lab abnormalities will be recorded as the AE.

All abnormal laboratory findings will be reviewed on a routine basis by the PI to identify potential safety signals. An abnormal lab not included on the toxicity table should be assessed in a similar fashion to the criteria above.

12.2 Investigator Assessment of Adverse Events

The investigator will assess all AEs with respect to severity (intensity or grade), and causality (relationship to study agent and relationship to research) according to the following guidelines.

12.2.1 Severity

The Investigator will grade the severity of each AE according to the "Division of AIDS (DAIDS) Table for Grading the Severity of Adult and Pediatric Adverse Events" most recent Version 2.1, July 2017, which can be found at: [https://rsc.tech-res.com/docs/default-source/safety/division-of-aids-\(daids\)-table-for-grading-the-severity-of-adult-and-pediatric-adverse-events-corrected-v-2-1.pdf](https://rsc.tech-res.com/docs/default-source/safety/division-of-aids-(daids)-table-for-grading-the-severity-of-adult-and-pediatric-adverse-events-corrected-v-2-1.pdf)

Because the DAIDS toxicity table does not have specific criteria for infusion-related reactions, we will use the following criteria, based on the Common Terminology Criteria for Adverse Events Version 4.0 (https://evs.nci.nih.gov/ftp1/CTCAE/CTCAE_4.03_2010-06-14_QuickReference_8.5x11.pdf). This is very similar to the grading criteria for "Cytokine release syndrome" that is part of the DAIDS table.

Table 2. CTCAE Infusion Reaction Severity Grading Criteria

Adverse event	Grade 1	Grade 2	Grade 3	Grade 4	Grade 5
Infusion-related reaction.	Mild transient reaction; infusion interruption not indicated; intervention not indicated.	Therapy or infusion interruption indicated but responds promptly to symptomatic treatment (eg, antihistamines, NSAIDs, narcotics, IV fluids); prophylactic medications indicated for ≤ 24 hrs.	Prolonged (eg, not rapidly responsive to symptomatic medication and/or brief interruption of infusion); recurrence of symptoms following initial improvement; hospitalization indicated for clinical sequelae.	Life-threatening consequences; urgent intervention indicated.	Death.

CTCAE = Common Terminology Criteria for Adverse Events; IV = intravenous; NSAID = nonsteroidal anti-inflammatory drug.

Some Grade 1 lab parameters on the DAIDS Toxicity Table fall within the NIH lab reference range for normal values. These normal values will not be reported as Grade 1 AEs.

12.2.2 Causality

Causality (likelihood that the event is caused by the study agent) will be assessed considering the factors listed under the following categories:

Definitely Related

- reasonable temporal relationship
- follows a known response pattern
- clear evidence to suggest a causal relationship
- there is no alternative etiology

Probably Related

- reasonable temporal relationship
- follows a suspected response pattern (based on similar agents)
- no evidence of a more likely alternative etiology

Possibly Related

- reasonable temporal relationship
- little evidence for a more likely alternative etiology

Unlikely Related

- does not have a reasonable temporal relationship
OR
- good evidence for a more likely alternative etiology

Not Related

- does not have a temporal relationship
OR
- definitely due to an alternative etiology

Note: Other factors should also be considered for each causality category when appropriate. Causality assessment is based on available information at the time of the assessment of the AE. The investigator may revise the causality assessment as additional information becomes available.

12.3 Investigator Reporting Responsibilities to the Sponsor

12.3.1 Adverse Events

AE data will be submitted to the IND sponsor when requested for periodic safety assessments, review of IND annual reports, review of IND safety reports, and preparation of final study reports.

12.3.2 Reporting to the Sponsor's Safety Office

12.3.2.1 Serious Adverse Events

All SAEs (regardless of relationship and whether or not they are also UPs) must be reported on the safety expedited report form (SERF) and sent to the Clinical Safety Office (CSO) by fax or email attachment. Deaths and immediately life-threatening SAEs must be reported to the CSO within 1 business day after the site becomes aware of the event. All other SAEs must be reported within 3 business days of site awareness.

CSO CONTACT INFORMATION:

Clinical Safety Office
[name]
[name]
[contact]
[contact]
E-mail: [contact]

SAEs that have not resolved by the end of the follow-up period are followed until final outcome is known. If it is not possible to obtain a final outcome for an SAE (e.g., the participant is lost to follow-up), then the reason a final outcome could not be obtained will be recorded by the investigator in CRIMSON and the SERF.

SAEs that occur after week 96 that are reported to and are assessed by the investigator to be possibly, probably, or definitely related to study drug must be reported to the CSO.

12.3.2.2 Unanticipated Problems

UPs that are also AEs must be reported to the CSO by fax or e-mail attachment using the NIH Problem Report Form no later than 7 calendar days of site awareness of the event. UPs that are not AEs are not reported to the CSO.

12.3.2.3 Events of Clinical Interest

The following ECIs must be reported to the CSO on a SERF within 3 business days of site awareness:

- Immune-mediated AEs other than hypothyroidism (Section 8.1).
- Opportunistic infections.
- An elevated AST or ALT lab value that is greater than or equal to 3 x ULN and an elevated total bilirubin lab value that is greater than or equal to 2 x ULN (excluding patients with Gilbert syndrome or those receiving atazanavir) and, at the same time, an alkaline phosphatase lab value that is less than 2 x ULN, as determined by way of protocol-specified laboratory testing or unscheduled laboratory testing. (These criteria are based on available regulatory guidance documents. The purpose of the criteria is to specify a threshold of abnormal hepatic tests that may require an additional evaluation for an underlying etiology.)
- Development of a new cancer.
- AEs that occur in reasonable temporal association with an overdose of pembrolizumab. (Overdose, in and of itself, without an associated AE, is reportable in an expedited fashion to the sponsor and IRB as a UP but is not considered an SAE. An overdose is defined as any dose greater than the protocol-defined dose of 200 mg.)

12.3.2.4 Pregnancy

Participants who inadvertently impregnate a partner after receiving study agent will be instructed to immediately inform the investigator. All pregnancies occurring within 120 days of pembrolizumab administration will be reported on the Pregnancy Notification/Outcome Form to the CSO within 1 business day from site awareness.

The investigator will make every effort to obtain pregnancy outcome data (e.g., delivery outcome, spontaneous or elective termination of the pregnancy). SAEs and the outcome of the pregnancy will be reported to the CSO within 3 business days of the site's awareness.

Although pregnancy itself is not an AE, events that meet SAE criteria during pregnancy, delivery, or in the neonate (eg, miscarriage, congenital anomaly/birth defect) are reportable on the SERF.

In the event of pregnancy, the following steps will be taken:

- Report to the CSO, IRB, and DSMB.
- Unblind participant.
- If participant received pembrolizumab, advise research participant that his partner should notify her obstetrician of study participation and study agent exposure.
- Maintain regular (e.g., monthly) contact with the participant to track the progress and outcome of the pregnancy, including any untoward events, AEs, and SAEs.

12.3.3 Investigator Reporting Responsibilities to the NIAID IRB

Unanticipated problems, non-compliance, and other reportable events will be reported to the NIH IRB as per Policy 801.

12.4 Sponsor's Reporting Responsibilities

SUSARs, as defined in Title 21 of the United States Code of Federal Regulations (CFR) Part 312.32 and determined by the IND sponsor, will be reported to FDA and all participating investigators as IND Safety Reports.

The IND sponsor will also submit an IND Annual Report of the progress of the investigation to the FDA as defined in 21 CFR 312.33.

12.5 Halting Rules for the Protocol

Halting the study requires immediate discontinuation of study agent administered for all participants and suspension of enrollment until a decision is made whether or not to continue enrollment and study agent administration.

The halting rules are:

- Any SAE that is unexpected and possibly, probably, or definitely related to the study agent;
- OR*
- 2 or more of the same or similar AEs in different participants that are Grade 3 or above (not including transient, subjective infusion-related symptoms such as malaise, fatigue, headache, or chills, or elevated total bilirubin in patients with Gilbert syndrome or those receiving atazanavir) and are possibly, probably, or definitely related to the study agent;
- OR*
- 2 or more Grade 2 or higher autoimmune events requiring corticosteroid therapy that are possibly, probably, or definitely related to the study agent;
- OR*
- Any safety issue that the PI and/or the CSO determines should halt the study.

The PI and/or CSO will determine if the study should be halted. In addition, the FDA may halt the study at any time following review of any safety concerns.

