12.5.1 Reporting a Study Halt

If a halting rule is met, then a description of the AE(s) or safety issue must be reported by the PI within 1 business day to the CSO, the IRB, and the DSMB by fax or email. The FDA will also be notified when a study is halted.

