12.7.3 Data and Safety Monitoring Board

The NIAID intramural DSMB includes independent experts that do not have direct involvement in the conduct of the study and have no significant conflicts of interests as defined by NIAID policy. The DSMB will review the study prior to initiation and twice a year thereafter and may convene additional reviews as necessary.

The DSMB will also review the safety data after 5 participants have been enrolled and followed for 90 days (this review may be one of the twice-yearly reviews); no additional participants will be enrolled until the DSMB recommends that study enrollment can be resumed.

The board will review the study data to evaluate the safety, efficacy, study progress, and conduct of the study. All SAEs, all UPs, and all IND Safety Reports will be reported by the PI to the DSMB at the same time they are submitted to the IRB or IND sponsor. The PI will notify the DSMB of any cases of intentional or unintentional unblinding as soon as possible. The PI will notify the board at the time pausing or halting criteria are met and obtain a recommendation concerning continuation, modification, or termination of the study. The PI will submit the written DSMB summary reports with recommendations to the IRB.

13 Site Monitoring Plan

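### One related death or life-threatening SAE of a kind already documented for pembrolizumab can be classed as expected and so meet no objective halting rule in 12.5

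*Combined protocol and SAP*

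**What the plan says.** Section 12.5 of the combined protocol and SAP lists four alternative halting rules:

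1. "Any SAE that is unexpected and possibly, probably, or definitely related to the study agent".
2. "2 or more of the same or similar AEs in different participants that are Grade 3 or above", related to the study agent, with some transient infusion symptoms and certain bilirubin elevations left out.
3. "2 or more Grade 2 or higher autoimmune events requiring corticosteroid therapy", again related.
4. "Any safety issue that the PI and/or the CSO determines should halt the study".

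The section closes with "The PI and/or CSO will determine if the study should be halted", and adds that the FDA may halt at any time.

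Two duties depend on these rules. Section 12.5.1 states: "If a halting rule is met, then a description of the AE(s) or safety issue must be reported by the PI". The recipients are the CSO, IRB and DSMB, with a deadline of 1 business day. Under 12.7.3, "The PI will notify the board at the time pausing or halting criteria are met and obtain a recommendation" on whether to continue, modify or terminate.

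Other provisions apply whether or not a rule is met. Deaths and immediately life-threatening SAEs go to the CSO within 1 business day (12.3.2.1). All SAEs go to the DSMB when they go to the IRB or sponsor, and the board "may convene additional reviews as necessary" (12.7.3). Immune-mediated events other than hypothyroidism go to the CSO within 3 business days (12.3.2.3). A medical monitor is in place (12.7.2). Enrolment is held once, for 90 days of follow-up and a DSMB review, after the first five participants (3.1).

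**The concern.** Rule 1 depends on the word 'unexpected', and no rule names death or a life-threatening event. Section 8.1 reports that immune-mediated pneumonitis has been fatal (3 of 10 drug-attributed deaths among 2799 patients) and that toxic epidermal necrolysis has been fatal. Table 1 gives pneumonitis as 0.3% Grade 4 and 0.1% Grade 5. An assessor could reasonably call such an event expected.

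The rules would then be stricter on two Grade 2 autoimmune events treated with corticosteroids, which meet rule 3, than on one related death, which need meet nothing objective. At stake is whether the next participant is infused before the DSMB has given a recommendation. This population makes that matter more. Section 4.4 describes the trial as the first safety study in HIV-infected patients without cancer, 8.2 says direct benefit is unlikely, and 8.1 says it is not known whether or how often the events seen in oncology will occur here.

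**Working it through.** **Step 1: rule logic.** Take one related Grade 4 or 5 pneumonitis, classed as expected, with no earlier qualifying event.

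| Rule in 12.5 | Needs | Met? |
|---|---|---|
| 1 | one SAE, related and unexpected | no, not unexpected |
| 2 | two similar related Grade 3+ AEs in different participants | no, count is 1 |
| 3 | two related Grade 2+ autoimmune events on corticosteroids | no, count is 1 |
| 4 | PI and/or CSO decision | only if they so decide |

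With no rule met, neither the 12.5.1 report nor the 12.7.3 recommendation is required.

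**Step 2: can it be classed as expected?** Section 12.5 does not define 'unexpected'. Section 12 refers to Policy 801 for event definitions, 12.4 to 21 CFR 312.32 and 1.2 to the Investigator's Brochure. None of these is in the documents. The text supports 'can', not 'must'.

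**Step 3: size (illustration only).** Assumptions: 15 treated, independent participants, and the Section 8.1 rates carried over from cancer patients, most of whom had multiple doses.

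The formula for at least one event is 1 - (1 - p)^15. It reproduces Section 14's own figure: 1 - 0.85^15 = 0.913.

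- At least one Grade 4-5 pneumonitis, p = 0.3% + 0.1% = 0.4%: 1 - 0.996^15 = 5.8%.
- Grade 2+ events of types that Appendix A treats with corticosteroids (Table 1, types taken as non-overlapping, '< 0.1' taken as 0 to 0.1): pneumonitis 2.6, colitis 1.5-1.6, hepatitis 0.5-0.6, hypophysitis 0.5-0.6, nephritis 0.2-0.3, Grade 3 hyperthyroidism 0.1. The sum is 5.4-5.8%.
- None of these in the other 14: 0.942^14 = 0.433 to 0.946^14 = 0.460.
- One Grade 4-5 pneumonitis with rule 3 not met through the others: 15 x 0.004 x (0.433 to 0.460) = 2.6-2.8%.
- The same for a pneumonitis death, p = 3/2799: 15 x (3/2799) x (0.433 to 0.460) = about 0.7%.

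A second event in the same participant is not modelled.

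**Step 4: timing.** A halt protects only people not yet infused, and events during the five-participant hold already face DSMB review. A simulation used 20 evenly spaced infusions with a 90-day gap after the fifth, a randomly chosen affected participant, and onset uniform over 1-5 months (8.1's typical range).

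| Infusion span | Outside the hold and before the last infusion | Step 3's 2.6-2.8% becomes | Mean not yet infused, both arms |
|---|---|---|---|
| 24 months (the 2-year accrual period) | 73% | 1.9-2.0% | about 8 |
| 12 months (assumed) | 51% | 1.3-1.4% | about 6.5 |

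Later onset, which 8.1 reports up to 21 months, would lower these figures.

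**The case against.** The strongest reply is that such an event would not pass unnoticed. The CSO hears of a death or immediately life-threatening SAE within 1 business day and the DSMB is told at the same time, essentially the 12.5.1 timetable. The CSO can halt without the PI. Once rule 4 is invoked it is itself a halting rule, so 12.5.1 and the DSMB recommendation follow. All of this stands. A reader might infer from 12.5 that a related death could go unreported to the DSMB, or that dosing would carry on; the documents do not support either. The gap is the missing obligation, not missing information or missing power to act.

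Second, expectedness rests on sources that cannot be seen here, and 8.1's statement that frequency in HIV is unknown could support calling a fatal event unexpected. Section 12.7.3 also mentions pausing criteria, which 12.5 does not list; they may sit in the safety review and communications plan (12.7.1), which is not in the documents. This limits the claim to what the protocol itself requires.

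Third, the illustration may be too high. Section 8.1 also lists arthritis 1.5%, uveitis 0.5%, myositis 0.5%, pancreatitis 0.3% and Guillain-Barre syndrome 0.1%, together 2.9%. If all needed corticosteroids (an upper assumption), the rule 3 set rises to 8.3-8.7%. The 2.6-2.8% then falls to 15 x 0.004 x (0.913^14 to 0.917^14) = 1.7-1.8%. That is a fair correction, but the rule logic does not depend on it.

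A reader might also infer that the closing PI/CSO sentence makes any rewording of rule 1 ineffective. It does not: 12.5.1 and 12.7.3 apply when a rule or criterion is met, whatever that sentence is taken to mean.

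**Conclusion.** The point holds as one of rule logic. A single related death or life-threatening SAE of a documented kind can be classed as expected and meet none of rules 1 to 3. No pause, 12.5.1 report to the IRB or DSMB recommendation is then required before the next infusion. Policy 801 may call for an IRB report of its own (12.3.3), but its content is not given.

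The probability is low. The 1.3-2.0% in the timing step is the chance that a qualifying pneumonitis occurs in the relevant window. It might be read as the chance that dosing continues after such an event, but that would also require the event to be classed as expected and the PI, CSO, FDA and any ad hoc DSMB review all to leave dosing running. The documents give no basis for putting a number on that. Rates from mostly multi-dose cancer patients may overstate the risk of one dose. This is an inexpensive improvement to a workable set of rules, justified by the severity of the event rather than its frequency.

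**What to change.** Change the first rule in 12.5 to: *Any death or life-threatening SAE that is possibly, probably, or definitely related to the study agent, whether or not expected; or any other SAE that is unexpected and possibly, probably, or definitely related.* This alone brings 12.5.1 and the 12.7.3 DSMB recommendation into force.

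To make the pause explicit, add only: *After a related death or life-threatening SAE, no further participant is infused until the DSMB recommendation is obtained.* PI/CSO discretion over the other rules can stay as it is.

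Sample size, visits and data are unchanged. The cost is a possible temporary pause. On the same cancer-patient rates, with 15 treated:

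- any drug-attributed death: 1 - (1 - 10/2799)^15 = 5.2%, although some of these may already count as unexpected;
- any Table 1 Grade 4-5 event, p = 0.5-0.9%: 1 - 0.995^15 = 7% to 1 - 0.991^15 = 13%.

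Events after the last infusion pause nothing, which lowers these figures; related life-threatening events outside Table 1 would add to them. Because causality is judged blind and 'possibly related' is a low bar (12.2.2), a placebo participant could also trigger a pause. At an assumed 1-2% per person, the chance among 5 is 1 - 0.99^5 = 4.9% to 1 - 0.98^5 = 9.6%. Emergency unblinding under 5.5.1, where its conditions are met, could shorten such a pause. Each participant receives one dose, so a pause delays new infusions and interrupts nobody's course of treatment.

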12.5.1 Reporting a Study Halt

If a halting rule is met, then a description of the AE(s) or safety issue must be reported by the PI within 1 business day to the CSO, the IRB, and the DSMB by fax or email. The FDA will also be notified when a study is halted.

12.5.2 Resumption of a Halted Study

The IND sponsor, in collaboration with the PI and the DSMB, will determine if it is safe to resume the study. The PI will notify the IRB of the decision on resumption of the study; the FDA will also be notified of this decision.

12.6 Withdrawal Criteria for an Individual Participant

An individual participant will be withdrawn for any of the following:

- An individual participant's decision. (The investigator should attempt to determine the reason for the participant's decision.)
- Non-compliance with study procedures to the extent that it is potentially harmful to the participant or to the integrity of the study data.
- Co-enrollment in a study with an investigational research agent other than expanded access antiretroviral medications.

- The investigator determines that continued participation in the study would not be in the best interest of the participant.

Prior to withdrawal, participants will be offered the opportunity to continue in the study for safety follow-up only, unless in the opinion of the investigator such follow-up would be potentially harmful to the participant.

Only participants who receive pembrolizumab or placebo will be included in the safety assessment. Once a participant has received the pembrolizumab or placebo infusion they will be included in the safety assessment regardless of early withdrawal.

Participants who withdraw prior to receiving the infusion of pembrolizumab or placebo, or who receive the infusion but withdraw prior to week 6 for reasons unrelated to safety (eg, personal decision) may be replaced with a participant who is assigned to the same study arm.

12.7 Safety Oversight

12.7.1 Safety Review and Communications Plan

A safety review and communications plan (SRCP) has been developed for the protocol. The SRCP is an internal communications document between the PI and the CSO, which delineates the safety oversight responsibilities of the PI, the CSO, and other stakeholders. The SRCP also includes the overall plan for conducting periodic safety surveillance assessments.

12.7.2 Sponsor Medical Monitor

A medical monitor, representing the IND sponsor (OCRPRO), has been appointed for oversight of safety in this clinical study. The sponsor medical monitor will be responsible for performing safety assessments as outlined in the SRCP.

